### 3.1 General Design

**Type of trial:** Pilot Feasibility trial

[figure not shown]
**Planned accrual period:** 24 months

**Planned follow-up period:** 12 months

**Planned enrollment:** Total of 50 patients

**Schema of the trial design, procedures, and stages:**

Patients with a head and neck region biopsy and diagnosis of HNSCC cancer who are planned to undergo definitive treatment by definitive radiation or up front surgery followed by adjuvant radiation. After informed consent is signed, patients will be administered metformin with dose escalation as tolerated\* until time of radiation.

\*Metformin (500 mg/day for 3 (+2 days) days followed by 500 mg twice daily for 3 days followed by 1000mg twice daily from day 6 (+2 days). Subjects will maintain 1000 mg twice a day dosing until two weeks post radiation. )

\*\* Placebo (1 tab taken BID) No ramp up phase

Participant's Follow-up. The participant's medical records will be reviewed every 3 months for 12 months to assess: Mucositis, xerostomia, fatigue and dysphagia

## 4.0 SUBJECT SELECTION AND WITHDRAWAL

### 4.1 Inclusion Criteria

1. Diagnosis: Subjects with a diagnosis of head and neck cancer biopsy proven, and who are candidates for radiation therapy
2. Age: Subjects must be  $\geq 18$  years of age and  $\leq 90$  years old.
3. Informed Consent: All subjects must be able to comprehend and sign a written informed consent document.

### 4.2 Exclusion Criteria

1. Subjects who are pregnant or may become pregnant during metformin administration. Pregnancy testing will be done in conjunction with preradiation protocols.
2. Subjects on metformin for any reason during the preceding 4 weeks.
3. Diabetic subjects are eligible if they are not taking metformin or insulin

4. Subjects who have received iodinated contrast dye must wait 12 hours prior to starting Metformin. If a CT scan with contrast is scheduled after screening and consent, the metformin cannot be taken until after the CT with contrast has been completed and they have waited 12 hours.
5. Patients with plasma creatinine level greater than 1.3 mg/dL.
6. Patients with plasma bicarbonate less than 22 mEq/L or history of lactic or any other metabolic acidosis.
7. Patients with history of congestive heart failure.
8. Patients with myocardial ischemia or peripheral muscle ischemia.
9. Patients with sepsis or severe infection.
10. Patients with history of lung disease currently requiring any supplemental oxygen treatment.
11. Patients scheduled for radiation less than 6 days from enrollment
12. Patients with history of hepatic dysfunction or hepatic disease and abnormal liver function tests. Patients who have a history of hepatic dysfunction or hepatic disease and normal liver function tests will be eligible to participate.
13. Patients with a current history (in the past 30 days) of having drinking which is defined in accordance with CDC definition as more than 8 drinks per week for women and more than 15 drinks per week for men. A standard drink contains .6 ounces of pure alcohol. Generally, this amount of pure alcohol is found in 12-ounces of beer, 8-ounces of malt liquor, 5-ounces of wine, 1.5-ounces or a “shot” of 80-proof distilled spirits or liquor (e.g., gin, rum, vodka, or whiskey). While on study, patients should limit their alcohol consumption to no more than 8 drinks per week for women and no more than 15 drinks per week for men. Patients who feel they cannot comply with this recommendation are not eligible

All medications are permitted except those that are contraindicated with metformin under current FDA recommendations. It is important to note that the medications that are contraindicated with metformin are contraindicated due to concern for theoretical interactions. The following is a list of medications identified as class C (monitor therapy) and class D (consider therapy modification) when treatment with metformin is considered:

Class C:

Carbonic anhydrase inhibitors  
Cephalexin  
agents  
Corticosteroids (orally inhaled)  
Corticosteroids (systemic)  
Dalfampridine  
Dofetilide  
Glycopyrrolate  
Lamotrigine  
Luteinizing hormone-releasing hormone analogs

Class D:

Cimetidine  
Iodinated contrast  
Somatropin

Pegvisomant  
Tropium

### **4.3 Gender/Minority/Pediatric Inclusion for Research**

This protocol will include women, minorities and pediatric cases (participants between 18 and 21 years). African Americans have a higher incidence of head and neck cancer and hence minority subjects are expected to be accrued at a higher rate than white subjects as compared to the population that Thomas Jefferson University Hospital serves. There is nearly a 3:1 predominance of males to females in this diagnosis. We will review accruals to this trial quarterly in the Head and Neck MDG and review the number of males and females accrued. If this deviates from the expected ratio we will review our actual patient ratio for that time and determine a remediation plan within the MDG to ensure accrual of women.

### **4.4 Subject Recruitment and Screening**

50 subjects will be recruited and we expect to recruit subjects between the ages of 18 and 90 with multiple comorbidities. Subjects will be recruited from the investigator or sub-investigator clinical practices. No advertisement will be conducted. Screening requirements include serum measurement of creatinine, bicarbonate, aspartate aminotransferase, alanine aminotransferase and alkaline phosphatase.

### **4.5 Early Withdrawal of Subjects**

#### 4.5.1 When and How to Withdraw Subjects

#### **Withdrawal criteria and procedures specifying when and how to withdraw subjects from the trial:**

Patients can withdraw at any time during the study if they no longer want to participate in the trial. If withdrawal occurs no further metformin administration will occur and patients will be required to return remaining metformin tablets which will be logged in to medication administration records and destroyed. If a subject withdraws consent to participate in the study, permission will be sought from the subject to record survival and progression for 2 years after enrollment. It is a high priority to try to obtain survival and progression free survival data on all subjects.

#### **Description of when a subject's participation in the trial may be discontinued:**

Specific reasons for discontinuing a subject from this study are:

1. Voluntary discontinuation by the subject who is at any time free to discontinue their participation in the study, without prejudice to further treatment.
2. Safety reasons as judged by the investigator.
3. Severe non-compliance to the protocol as judged by the investigator.
4. Incorrect enrollment of the subject.
5. Subject lost to follow-up
6. Death

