| 
Statistical Methodology
 | 
The primary objective of the study is to assess the impact of metformin on cytokine and exosome profiles. All subjects from whom blood and saliva samples are obtained both pre-, during and post-treatment will be included in the primary analyses. Change in cytokine profiles will be evaluated using mixed effects linear regression.
 
Analysis of secondary outcomes will be primarily descriptive. The distribution of swallowing function and mucositis scores will be summarized. The objective response rate will be estimated along with an exact 95% binomial confidence interval.
   |
| 
Schema
                  | 
50 HNSCC patient candidates for adjuvant or neoadjuvant radiation
  <pre> graph TD     A[50 HNSCC patient candidates for adjuvant or neoadjuvant radiation] --> B[Pre-metformin blood and saliva samples]     B --> C[Randomized Metformin Treatment* (n=25) vs Placebo** Treatment (n=25)]     C --> D[external beam radiation (sample collected halfway through)]     D --> E[Post-metformin blood and saliva sample]   </pre> 
*Metformin (500 mg/day for 3 (+ 2 days) days followed by 500 mg twice daily for 3 days followed by 1000mg twice daily from day 6 (+2 days). Subjects will maintain 1000 mg twice a day dosing until two weeks post radiation. )
 
** Placebo (1 tab taken BID) No ramp up phase
 |

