#### **4.5.2 Data Collection and Follow-up for Withdrawn Subjects**

Survival data will be collected for subjects that withdraw prematurely as well as progression of disease information. If a subject withdraws consent to participate in the study, permission will be sought from the subject to record survival and progression for 1 year after enrollment. It is a high priority to try to obtain survival and progression free survival data on all subjects lost to follow-up. Subjects will be called by phone at least on three occasions, phone calls at least twice will be carried out to the next-of-kin and certified letters will be sent twice. If follow-up is not obtained after the previously listed attempts have been carried out the subject will be considered lost to follow-up.

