#### **5.9 Blinding of Study Drug**

The bottle will be non-descript and contain either metformin or placebo depending on randomization. Patients will be blinded to which pill (metformin or placebo) they will receive. Pill distribution will be completed by the pharmacist who will not be blinded. Principal Investigator and care providers making assessments will not be blinded.

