## **7.0 STATISTICAL PLAN**

### **7.1 Analysis for Primary Outcome**

Mixed effects linear regression will be used to model longitudinal measurements of each cytokine. Measurement time will be treated as a categorical variable and fixed effects in the model will include randomization assignment, time, and randomization by time interaction. A linear contrast will be used to estimate the difference in randomization groups with respect to mean change from baseline to

post-treatment. Significance of this difference will be calculated for each cytokine and p-values will be adjusted using the Benjamini and Hochberg procedure to control the false discovery rate at 5%. Cytokine levels will likely need to be log-transformed prior to analysis to meet model assumptions.

Longitudinal measurements of exosomes will also be modeled using mixed effects linear regression in the same fashion. This analysis is treated as separate from the cytokine questions and the p-value will not be adjusted.

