## 7.3 Subject Population(s) for Analysis:

All randomized participants with any data will be included in the analysis.

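### The plan does not say that endpoint sampling continues after study drug is stopped or the investigator discontinues a patient, so Visit 3 samples could be lost avoidably and possibly by arm

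*Combined protocol and SAP*

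**What the plan says.** The list in 4.5.1 opens with "Specific reasons for discontinuing a subject from this study are", so it concerns leaving the study and not only stopping tablets. Two of its six entries rest on the investigator's judgement: "Safety reasons as judged by the investigator" and "Severe non-compliance to the protocol as judged by the investigator".

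Section 4.5.2, on withdrawn subjects, says: "Survival data will be collected for subjects that withdraw prematurely as well as progression of disease information". It names no other outcome. The endpoints in 2.3 and 2.4 are the cytokine and exosome profiles, mucositis, dysphagia, xerostomia and fatigue; survival and progression are not among them.

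Stopping drug also exists as a separate idea. The toxicity rules in 1.6, 5.3, 6.2 and 6.3 stop treatment, and 8.4 allows study drug to be stopped at the physician's discretion. None of these, nor the visit schedule in 6.1, nor Appendix A, says what is collected afterwards.

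On the analysis, 7.1 states: "A linear contrast will be used to estimate the difference in randomization groups with respect to mean change from baseline to" post-treatment. Section 7.3 states: "All randomized participants with any data will be included in the analysis". The Study Summary is narrower: "All subjects from whom blood and saliva samples are obtained both pre-, during and post-treatment will be included in the primary analyses". On blinding, 5.9 states: "Principal Investigator and care providers making assessments will not be blinded".

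**The concern.** The main contrast is change from baseline to post-treatment, and the post-treatment sample is taken at Visit 3, two weeks after radiation ends. Visit 2 falls in the third week of radiation and includes a medication inventory. A judgement of severe non-compliance, or a safety decision, can therefore come before the sample the contrast depends on. If the patient then leaves the study, the plan makes no provision for taking that sample.

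Two features make it possible that such losses differ between arms. The person making the judgement is not blinded. The regimens also differ: metformin builds up to two tablets twice daily and has gastrointestinal upset as its most common toxicity (1.6, 5.3), while placebo is one unit twice daily with no build-up (5.2, 5.11). If patients who leave also have a different inflammatory course from those who stay, the comparison of arms is biased as well as less precise. With 25 patients per arm, and no dropout allowance or missing-data assumption in section 7, each lost sample counts.

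**Working it through.** **1. Reproduce the plan's figure.** Inputs from 7.4: 25 per arm, two-sided alpha 0.05, 80% power, exosome effect 0.81 SD. A two-sample t-test calculation gives a detectable effect of 0.809 SD, and power of 80.1% at 0.81 SD. The stated figure is reproduced, with all 25 patients per arm contributing.

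**2. Trace what happens to a patient.**

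| Event | Where | Collection provided for afterwards |
|---|---|---|
| Drug stopped under the toxicity grades or at the physician's discretion | 1.6, 5.3, 6.2, 6.3, 8.4 | Not stated; participation is not said to end |
| Investigator discontinues the patient from the study | 4.5.1 | Survival and progression (4.5.2) |
| Adverse events | 8.1 | Reported to 30 days after the last dose |
| Blood, saliva, mucositis, questionnaires after either kind of discontinuation | 6.1, Appendix A | Not stated |

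**3. Bias if loss is selective.** Let f1 and f0 be the proportions without a Visit 3 sample in the two arms. Let s be the difference, in SD of the change score, between lost and retained patients, taken as equal in both arms. The mean over everyone randomized in an arm is (1 − f) × m + f × (m + s) = m + f × s, where m is the mean in retained patients. If earlier samples do not predict the difference, the contrast is biased by:

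bias = (f1 − f0) × s

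The documents give no dropout rate, so f and s are assumptions, with s from 0.5 to 1.0.

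- *Low case, 5-point excess.* The nearest figure in the documents is that gastrointestinal upset leads fewer than 5% of users to stop metformin (1.6, 5.3). This concerns stopping drug in general use, not leaving this trial. 0.05 × 0.5 = 0.025 SD; 0.05 × 1.0 = 0.05 SD.
- *High case, 16-point excess.* 5 of 25 lost against 1 of 25: 0.20 − 0.04 = 0.16. Then 0.16 × 0.5 = 0.08 SD; 0.16 × 1.0 = 0.16 SD.

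Against the 0.81 SD exosome effect, the range is 0.025 / 0.81 = 3% to 0.16 / 0.81 = 20%.

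**4. Precision.** The same t-test calculation, treating patients without Visit 3 as contributing nothing:

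| Patients with Visit 3 | Detectable effect, 80% power |
|---|---|
| 25 v 25 | 0.81 SD |
| 24 v 25 | 0.82 SD |
| 20 v 24 | 0.87 SD |

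These are upper limits for each split, because the mixed model still uses the earlier samples of patients who leave.

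**The case against.** The strongest reply is that the plan already handles most of this. Stopping drug is treated separately from leaving the study, so a patient who cannot tolerate tablets is managed by the toxicity grades and is not thereby removed. Section 4.5.1 sets a threshold of severe non-compliance and is permissive; nothing shows that a poor pill count at Visit 2 would meet it. Section 4.5.2 says what will be collected and does not forbid more. Section 7.3 expects incomplete data, and the mixed model in 7.1 uses baseline and week-3 samples and is valid if data are missing at random. This is also a 50-patient pilot.

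Much of that stands. A reader might infer that the protocol orders sampling to stop; the text is silent, which is an omission and not an instruction. A reader might infer that every patient who stops tablets is lost; that would need a further decision by the investigator. A reader might also infer that the result will favour metformin. No document shows that removed patients are more inflamed, or that removal will be commoner in one arm, so neither the direction nor the fact of selective loss is established.

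What does not stand is the conclusion that nothing needs changing. An any-data rule cannot supply a sample that was never taken. A patient with only a baseline sample adds almost nothing to a change contrast. Missing at random is doubtful where an unblinded investigator removes patients for tolerability or compliance. The Study Summary's requirement for all three samples, if followed, would also discard the partial data on which this defence relies.

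**Conclusion.** The point holds as a gap in the rules for data collection. The plan allows an unblinded investigator to end participation for safety or severe non-compliance, and makes no provision for collecting the primary or secondary endpoints afterwards or after drug alone is stopped. The resulting loss of Visit 3 samples would be avoidable and could be related to arm.

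Its size cannot be known from the documents. The bias figures (0.025 to 0.05 SD at a 5-point excess loss, 0.08 to 0.16 SD at 16 points) assume lost patients differ by 0.5 to 1.0 SD in a way earlier samples do not predict. The high case uses a 20% loss in one arm, at least four times the under-5% cessation figure in the documents, and should be read as an illustration. The rise in the detectable exosome effect to at most about 0.87 SD assumes 20 v 24 with no use of partial data.

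The documents do not support saying that 7.3 is invalid or that the trial is biased towards metformin. They support saying that 7.3's aim depends on samples the protocol does not undertake to collect. That can be put right cheaply now, whereas a missed sample cannot be recovered later.

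**What to change.** - In 4.5.1 and 4.5.2, state that stopping study drug for any reason, including non-compliance, does not by itself end participation in the study.
- State that randomized patients keep the scheduled Visit 2, Visit 3 and 3-monthly collection of blood, saliva, mucositis scores and questionnaires, unless they withdraw consent to that collection or the investigator judges the collection itself unsafe.
- Remove non-compliance with study drug as a reason to stop collecting data.
- Ask patients who withdraw consent to treatment whether they will still give the Visit 3 sample.
- Align the Study Summary's analysis population with 7.3.

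The clinical rules for stopping drug are left unchanged.

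The cost is an amendment to the protocol and consent wording, plus a few more assays and study visits for patients off drug. The 3-monthly samples are already taken at regular appointments. Visits 2 and 3 are listed as study visits, and 6.1 leaves the place of radiation open, so some extra attendance should be expected.

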#### **4.5.2 Data Collection and Follow-up for Withdrawn Subjects**

Survival data will be collected for subjects that withdraw prematurely as well as progression of disease information. If a subject withdraws consent to participate in the study, permission will be sought from the subject to record survival and progression for 1 year after enrollment. It is a high priority to try to obtain survival and progression free survival data on all subjects lost to follow-up. Subjects will be called by phone at least on three occasions, phone calls at least twice will be carried out to the next-of-kin and certified letters will be sent twice. If follow-up is not obtained after the previously listed attempts have been carried out the subject will be considered lost to follow-up.

### **5.0 STUDY DRUG/THERAPY**

#### **5.1 Description**

Metformin is a biguanide drug currently approved for the treatment of type 2 diabetes mellitus by the FDA. It is currently being investigated in multiple cancer treatment trials.

#### **5.2 Treatment Regimen**

Metformin is the therapeutic agent in the protocol. The initial starting dose will be 500mg orally daily for 3 (+2 days) days which then will be increased to 500 mg twice daily and, if tolerated, further increased to 1000mg twice daily after day 6 (+ 2 days). Patients will maintain 1000 mg twice a day dosing until 2 weeks after completing their radiation. This dose schedule has been shown to be well tolerated.

The placebo will be dosed as 1 tab BID and will not have a dose escalation.

#### **5.3 Risks**

##### **Summary of known and potential risks and benefits, if any, to subjects:**

Metformin's most serious toxicity is lactic acidosis, occurring in three of 100,000 patient-years of use. Risk is significantly reduced when metformin use is avoided in those patients with hepatic, cardiac, or renal compromise and in those age 80 years or older. However, metformin's risk of lactic acidosis may be overstated since the recent evaluation of metformin associated lactic acidosis cases from

347 trials showed that the risk of lactic acidosis with metformin was not significantly increased compared with other antiglycemic agents. Minor gastrointestinal upset is the most common toxicity, leading to cessation of therapy in less than 5% of individuals. Metformin does not cause hypoglycemia. The study is designed to assess as the primary end-point the effects of metformin on cytokines with short term administration and not to assess if metformin improves outcomes in head and neck cancer and hence it is unlikely to improve the clinical outcome of the subjects enrolled in this study.

**Rules for dose modification: Toxicity monitoring, dose modification and treatment of complications:**

Particular attention will be paid in the first three days of treatment. Patients will take 500mg/day for 3 days (+2 days). From day 4, 500mg twice daily and then in 3 days (+2 days) dose escalation to 1000mg twice daily will be achieved. This will be taken until the day before surgery after dinner. A phone call on the day of each dose escalation will be made in order to evaluate the tolerability of the drug and also weekly thereafter. Patients will be instructed to contact the clinical investigators should any toxicity occur during the study.

Metformin will not be started if CT scan with intravenous contrast is scheduled. After the scan they will be instructed to start the metformin the following day. This approach is more stringent than the most recent recommendation of the American College of Radiology which does not recommend holding metformin in the absence of comorbidities (renal insufficiency, liver dysfunction, alcohol abuse, cardiac failure, myocardial or peripheral muscle ischemia, sepsis or severe infection) which are exclusion criteria for this clinical trial.

Toxicity will be evaluated using the most recent version (version 3) of the NCI toxicity criteria, i.e. the NCI Common Terminology Criteria for Adverse Events (CTCAE) version 4.0. The CTCAE provides descriptive terminology and a grading scale for each adverse event listed. A copy of the CTCAE can be found at <http://ctep.cancer.gov>.

Grade 1 toxicity: Patient will be maintained on full dose.

Grade 2 toxicity: Dose will be reduced by 50% until grade 1 or lower. If symptoms are not resolved within 3 days the treatment will be discontinued definitively.

Grade 3 toxicity (probably or definitely drug related): Treatment will be interrupted and toxicity reassessed daily. If toxicity improves to grade 2, dose will be reduced by 50%.

Grade 4 toxicity (probably or definitely drug related): Treatment will be discontinued definitively.

In case of grade 1 or 2 diarrhea (the most frequent side effect) a concomitant administration of loperamide will be provided.

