### **2.2 Secondary Objective:**

- Assess safety and tolerability of metformin treatment in subjects undergoing external beam radiation treatment for head and neck cancer.

- To determine the effect of metformin treatment on symptoms of **xerostomia** as assessed by the Xerostomia Questionnaire (XQ)
- To determine the effect of metformin treatment on symptoms of **mucositis** as assessed by WHO classification
- To determine the effect of metformin treatment on symptoms of **dysphagia** as assessed by the MD Anderson Dysphagia Inventory
- To determine the effect of metformin treatment on symptoms of **Fatigue** as assessed by the Multidimensional fatigue inventory (MFI).

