### **6.1 Study Visit Schedule**

Screening: Trial Coordinator will screen the office charts for possible inclusion in the trial. Labs for the screening part will be available from pre-admission testing that is standard of care.

Visit 1: Subjects that meet the inclusion criteria after reviewing the initial biopsy, laboratory data and clinical chart will be approached the day of their follow up after initial biopsy. The study coordinator will meet with the prospective candidates and go over the protocol, answer questions and obtain informed consent. If the subject is agreeable to the study, a physical exam will be performed, blood and saliva will be collected, and participant will be randomized.

Metformin/placebo Instructions on how to take study drug will be given and times for follow up phone calls for tolerability and safety will be arranged with participants. Participants will be instructed to call with any side effects or adverse events that occur in the interim of the follow up phone calls. The exact date to start the metformin will be determined this visit based on the planned start of radiation. Subject will be instructed to start taking the metformin/placebo at any point from 1 to 7 days from the start of radiation.

Quality of life measures including the EORTC QLQ – H&N35, mucositis score, Multidimensional fatigue inventory and the Xerostomia Questionnaire (XQ) will be administered on an iPad through the website ([https://az1.qualtrics.com/jfe6/preview/SV\\_87y9lyJ0sFo8oJv](https://az1.qualtrics.com/jfe6/preview/SV_87y9lyJ0sFo8oJv)). Patients will be identified only by an ID number.

Visit 2: Subjects will come in during the 3rd week of their radiation for blood draw, saliva collection, physical exam, quality of life questionnaires and tolerability assessment. An inventory of medication will also be taken to assess compliance. Location of radiation is not dictated by this protocol.

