## **8.2 Recording of Adverse Events**

At each contact with the subject, the investigator will seek information on adverse events by specific questioning and, as appropriate, by examination. Information on all adverse events will be recorded immediately in the source document, and also in the appropriate adverse event module of the case report form (CRF). All clearly related signs, symptoms, and abnormal diagnostic procedures results should be recorded in the source document, though should be grouped under one diagnosis.

All adverse events occurring during the study period will be recorded.

The clinical course of each event will be followed until resolution, stabilization, or until it has been determined that the study treatment or participation is not the cause. Serious adverse events that are still ongoing at the end of the study period will be followed up to determine the final outcome. Any serious adverse event that occurs after the study period and is considered to be possibly related to the study treatment or study participation will be recorded and reported immediately.

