- C. C Blood samples, saliva samples, and quality of life questionnaires will be collected every 3 months for the first year post treatment. Collection will occur at participant's regularly scheduled appointments.
- D. D Quality of life surveys include: EORTC QLQ – H&N35, mucositis score, Multidimensional fatigue inventory and the Xerostomia Questionnaire (XQ). All questionnaires will be administered online via an iPad provided at the visit.
- E. E Visit will be 2 weeks after the completion of radiation therapy.
- F. F Patients will be seen at regularly scheduled appointments every 3 months for the 1st year post treatment. Participant's medical records will be reviewed every 3 months for 12 months
- G. G The initial starting dose of metformin will be 500mg orally daily for 3 (+2 days) days which then will be increased to 500mg twice daily and, if tolerated, further increased to 1000mg twice daily after day 6 (+2 days). Patients will maintain 1000mg twice daily dosing until 2 weeks after completion of radiation. If patient must have CT scan with intravenous contrast, metformin will be held and participant will be instructed to start metformin the day following the scan.
- H. H Placebo will be given as 500mg tablets twice daily with no dose escalation

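### Tolerability calls are timed to dose escalations, which placebo does not have, so early adverse events may be asked about once or twice more on metformin

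*Combined protocol and SAP*

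**What the plan says.** All references are to the combined protocol and SAP.

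- **Call rule.** The dose-modification text in section 5.3 states "A phone call on the day of each dose escalation will be made in order to evaluate the tolerability of the drug". Further calls follow each week. Section 1.6 has the same rule. No other text sets days for these calls.
- **Metformin.** There are two escalations, from once to twice daily and then to the full dose. Section 5.3 puts it as "From day 4, 500mg twice daily and then in 3 days (+2 days) dose escalation to 1000mg twice daily will be achieved".
- **Placebo.** Section 5.2 states "The placebo will be dosed as 1 tab BID and will not have a dose escalation". Note H to Appendix A agrees: "Placebo will be given as 500mg tablets twice daily with no dose escalation". The schema in the Study Summary and section 3.1 also show no ramp-up.
- **Visit 1.** In a paragraph covering metformin and placebo together, section 6.1 says that "times for follow up phone calls for tolerability and safety will be arranged with participants". It gives neither number nor days.
- **Elicitation.** Section 8.2 states "At each contact with the subject, the investigator will seek information on adverse events by specific questioning".
- **Scheduled assessments.** Appendix A lists adverse-event assessment at Visit 1, Visit 2 (third week of radiation), Visit 3 and follow-up, the same in both arms. It has no phone-call row.
- **Objective.** The first item in section 2.2 is "Assess safety and tolerability of metformin treatment in subjects undergoing external beam radiation treatment for head and neck cancer".

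**The concern.** A placebo arm helps the safety reading only if both arms are asked about symptoms equally often. Patients starting head and neck radiation have background complaints that can resemble the gastrointestinal effects the plan expects from metformin. Here the one rule that fixes call days depends on an event that placebo patients never have, and the weekly series that follows has no defined starting point for them.

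The affected period is the ramp-up, when mild, transient complaints are most likely to be put down to the drug. A placebo patient with the same complaint may have recovered by Visit 2 without being asked. Section 5.9 leaves the investigator and assessing care providers unblinded, so blinding gives no protection against unequal questioning. The safety committee described in section 8.5.2 reviews adverse-event listings, and readers of the results will compare the arms whether or not a test is planned.

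**Working it through.** The plan gives no figure for the number of calls, so the check is a count from the text followed by an illustration.

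**Timing.** From section 5.3, the escalations fall near day 4 and day 4 + 3 = day 7. If both +2-day windows are used, the second falls on day 4 + 2 + 3 + 2 = day 11. Section 1.6 labels the second step day 6, which makes no difference here. The third week of radiation begins 14 days after radiation starts. Section 6.1 starts study drug 1 to 7 days from the start of radiation; read as before radiation, Visit 2 is at the earliest 14 + 1 = 15 to 14 + 7 = 21 days after first dose. Section 1.6 starts it one to two weeks before, giving 21 to 28 days. On either reading both escalation calls precede Visit 2, and calls are the only scheduled inquiry in between. If section 6.1 meant after the start of radiation, Visit 2 could come 7 to 13 days after first dose, and the window would be shorter.

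**Number of calls.** Assume escalation calls near days 4 and 7, then weekly calls from day 14 to the end of treatment. Section 1.6 gives 8–10 weeks of exposure, at most 12. Metformin has 2 + 7 = 9, 2 + 9 = 11 and 2 + 11 = 13 calls at 8, 10 and 12 weeks. The placebo count depends on a rule that the plan does not state:

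| Placebo rule assumed | Placebo calls (8, 10, 12 weeks) | Metformin excess | Contact ratio with Visits 2 and 3 |
|---|---|---|---|
| (a) Weekly, same days as metformin, from day 14 | 7, 9, 11 | 2 | 11/9 = 1.22, 13/11 = 1.18, 15/13 = 1.15 |
| (b) Weekly from day 7 | 8, 10, 12 | 1 | 11/10 = 1.10, 13/12 = 1.08, 15/14 = 1.07 |

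The whole excess lies in the first week or so.

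**Possible effect on reported rates.** Let q be the chance that one call records a background complaint, with no drug effect and independent calls. With two calls on metformin and one on placebo, as in (b), the gap is [1 − (1 − q)²] − q = q(1 − q).

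- q = 5%: 0.0975 − 0.05 = 0.0475, or 25 × 0.0475 = 1.2 patients.
- q = 10%: 0.19 − 0.10 = 0.09, or 25 × 0.09 = 2.25 patients.

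The documents give no value for q. The nearest figure is 1–5% in section 1.6, for metformin side effects rather than background. At q = 1% the gap is 0.0199 − 0.01 = 0.0099, or 0.25 patients.

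A second illustration does not need independent calls. Assume a true rate of 20% for a transient early event in both arms, captured 90% of the time on metformin and 80%, 60% or 40% on placebo. Expected reports per 25 are 25 × 0.20 × 0.90 = 4.5 against 4.0, 3.0 or 2.0.

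**Sample size.** Section 7.4 states a detectable exosome effect of 0.81 SD with 25 per group. A two-sample t-test calculation gives 0.809. Call timing does not enter it.

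**The case against.** The strongest reply is section 6.1. It arranges tolerability and safety calls for metformin and placebo patients alike and tells both to phone in with side effects between calls. A reader might infer from sections 1.6 and 5.3 that placebo patients receive no calls at all. Section 6.1 contradicts that, and the inference should not be drawn. Nor is it established that they get none in the first week. Using two calls against none there would give gaps of 9.75 and 19 percentage points at q = 5% and 10%, but that presumes reading (a), which the text does not state.

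A reader might also conclude that the safety comparison is biased. Section 7 defines no between-arm adverse-event comparison, section 7.2 makes the secondary analysis mainly descriptive, and section 2.2 words the aim around metformin. What remains is a risk to descriptive rates. Both arms share the visit-based assessments, and repeated calls about a persisting symptom are not independent, so the illustration may overstate the gap.

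Two further inferences add little. The call pattern could reveal the arm to the caller, but section 5.9 already leaves assessors unblinded. More reports could lead to more dose reductions, but grade 1 events keep the full dose, and the documents do not allow the effect at grade 2 to be sized.

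What the reply does not remove is the gap in the text. Section 6.1 gives no days, so staff looking for them find only a rule that placebo patients cannot trigger.

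**Conclusion.** The concern holds as a risk of unequal early ascertainment. The call rule as written gives metformin about one or two more solicited adverse-event contacts in roughly the first week of dosing, ahead of Visit 2. The likely direction is against metformin, mainly for mild and transient events.

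The size rests on assumptions. At an assumed q of 5–10%, with independent calls and one placebo call in the window, about 5–9 percentage points of the early difference (1–2 patients of 25) could arise with no drug effect; at q = 1% it is negligible. With 25 per arm, one or two patients can change the impression of tolerability. The point does not touch the cytokine or exosome analyses or the sample size. It is worth correcting because the remedy is cheap, not because a bias has been shown.

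**What to change.** Reconcile sections 1.6 and 5.3 with section 6.1 so that both arms have one stated contact schedule:

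- Keep the escalation-day calls on metformin. They check tolerability at the actual dose step, and replacing them with fixed days could separate the check from that step.
- Add matching placebo calls on the corresponding study days. This needs one agreed statement of those days, which sections 1.6 and 5.3 do not yet give consistently.
- Count the weekly calls from first dose in both arms.
- Use one scripted adverse-event checklist for every call.
- Add a phone-call row to Appendix A covering both arms.
- Report the number of solicited contacts per patient by arm beside the adverse-event rates.

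Under the counting assumptions above, the difference in scheduled calls falls from one or two to zero. The cost is about two short calls for each of 25 placebo patients, 2 × 25 = 50 in all, made by staff already calling, and a few lines of text. No dosing rule changes.
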